9 DATA ANALYSIS / STATISTICAL METHODS

Detailed methodology for summary and statistical analyses of the data collected in this study will be documented in a Statistical Analysis Plan (SAP). This separate document will be finalized prior to study unblinding and conduct of any statistical analyses. The SAP may modify and will take precedence over the plans outlined in the protocol; however, any major modifications or modification of the primary endpoint definition and/or its analysis will also be reflected in a protocol amendment.

The primary efficacy outcome will be the difference in SIB total score from baseline at Week 28 between treatment arms, after two 12-week courses of the study drug have been given.

9.0 Sample Size Determination

The power analysis for the current study is based on a minimum clinically significant difference in mean total SIB scores from baseline of 4 points between the placebo and bryostatin arms at Week 28. Since the analysis of this primary outcome is based on a linear regression model that utilizes the total SIB scores at Weeks 0, 5, 9, 13, 15, 20, 24, and 28, a difference of approximately 1.5 points per week in the slope of total SIB scores between the placebo and bryostatin arms yields the clinically meaningful difference of 4 points at Week 28. As these measures of total SIB scores are correlated within individual, methods of GEE will be used to estimate the regression parameters of the linear regression model of total SIB score regressed on time. GEE power analysis is based on the following equation:

$$m = \frac{2(z_{\alpha/2} + z_b)^2 \sigma^2 (1 - \rho)}{n s_x^2 d^2} \quad \text{Eq 1}$$

In equation 1, m is the number of patients per group, $z_{\alpha/2}$ is the type I error rate, z_b is the type II error rate, σ is the standard deviations of the error (residual) terms, ρ is the within person correlation of total SIB scores over time within a person, n is the time points where the total SIB score is obtained, s_x^2 is the variance of the X predictor variable (i.e. time in the current scenario), and d is the difference in slopes over time in total SIB measures from baseline between the placebo and bryostatin arms.¹⁷

Based on the data from the NTRP101-202 study among patients without memantine, we obtained an estimate for $\sigma = 5.3$. In addition, the NTRP101-204 study will have SIB total scores measured at $n = 8$ timepoints, giving a value of $s_x^2 = 127$. Assuming a total of 100 patients (50 patients per arm), a two-sided type I error rate of 0.05 (i.e. $z_{\alpha/2} = 1.96$), and moderate within person correlation of outcome measures (i.e. $\rho = 0.5$), we will have > 99% power to see a difference in slopes over time of $d = 0.15$ points per week. In addition, we will have > 99% power to see this difference if we experience a 20% drop out.

9.1 Statistical Methods

The Safety Analysis Set (SAS) is defined as all randomized subjects who received any study medication (either partial or completed infusions of bryostatin or placebo).

CONFIDENTIAL

The Full Analysis Set (FAS), consistent with the modified intention-to-treat (mITT) principles, is defined as all randomized subjects who received at least one dose of study medication and who have at least one post-baseline efficacy assessment.

The Per Protocol Analysis Set (PP) is defined as all patients completing the study without major protocol deviations. To be included, subjects must have received at least 11 of the 14 doses (80%).

The Completer Analysis Set (CAS) is defined as all randomized subjects who completed two courses of treatment, and who have a week 28 SIB assessment.

Demographics data collected will include age, sex, race, ethnicity, height, and body weight and will be summarized by treatment group using descriptive statistics for both the SAS and FAS populations.

Medical history, neuroimaging, prior and concomitant medications, existing disease, years since AD onset and diagnosis, baseline medical conditions, and baseline safety and neuropsychological assessments will be summarized descriptively by treatment group for both the SAS and FAS populations.

Subject disposition will be summarized by treatment group and will include numbers screened, randomized, dosed and withdrawn with reason for withdrawal.

9.2 Exploratory Analysis

Descriptive statistics by visit and randomized treatment group will be provided for all efficacy data. These descriptive statistics will include the mean, median, SD, maximum and minimum for continuous variables, and frequencies, percentage, and tabulations for categorical variables. Summary statistics will also be performed on both the patient demographics and patient clinical characteristics. Exploratory plots of the data will also be created, including box plots and histograms, in order to determine the distribution of these data as well as to identify any unusual or outlying observations.

9.3 Safety Analysis

The SAS population will be used for all safety analyses with treatment group determined by the treatment actually received. AEs, safety laboratory, ECGs, physical exam and vital signs data will be presented in tabular format and summarized descriptively by treatment group. No formal hypothesis testing will be carried out on these safety assessments. Incidence and severity of AEs will be summarized by treatment dose using System Organ Class (SOC). AEs will be coded according to standard MedDRA terms.

C-SSRS responses will be mapped onto the Columbia-Classification Algorithm of Suicide Assessment (C-CASA) scale, and the frequency distribution of the C-CASA scores will be tabulated by treatment group and study visit. No hypotheses associated with the C-SSRS or C-CASA scales will be tested.

CONFIDENTIAL

9.4 Analysis of Primary Efficacy Endpoint

The treatment difference in the primary efficacy endpoint of total SIB scores from baseline at Week 28 will be determined from a regression model that utilize SIB values taken at Weeks 0, 5, 9, 13, 15, 20, 24, 28 and 30. As SIB is a continuous outcome measure, a regression model will be used to estimate the treatment difference in mean SIB from baseline at Week 28. Both linear and non-linear terms will be considered in these regression models. Since correlation of SIB measures over time within a patient will be present, regression coefficients will be estimated using the generalized estimating equations (GEE) methodology.¹⁸ GEE regression models are used to appropriately estimate the population average effects from a sample of individuals when the correlations of SIB measures within individuals are unknown. The GEE method accounts for the correlation structure in the model. However, the estimates of model coefficients and their standard errors models are unbiased even if the working correlation model is incorrectly specified. The primary analysis will be conducted on FAS population. The PP and CAS populations will be used as supportive analyses. All statistical tests for efficacy will be two-sided tests, with $\alpha=0.05$.

Based on the review of patients not treated with memantine in the NTRP 101-203 clinical trial, the expected number of patients who will drop out of the study prematurely will not be significant. However, missingness will be accounted for using weighted GEE methods.¹⁹ The GEE regression models will be carried out in SAS/STAT PROC GEE version 13.2. This SAS procedure will allow for implementation of weighted GEE methodology that can account for data missing a random. One additional patient may be randomized for each patient who discontinues the study prior to the primary endpoint (Week 28, Day 196).

9.5 Secondary Efficacy Endpoints

Multiple comparisons arising from the listed secondary outcomes will be controlled by using the false discovery rate. This procedure will allow control of the type I error rate over the set of secondary outcomes that is less stringent than controlling for multiple comparisons using a familywise error rate (e.g. Bonferroni correction).

9.5.1 SIB total score from baseline at the Week 42 follow-up visit

Treatment differences in SIB total score from baseline at Week 42, for subjects who completed that visit, will be estimated using an ANCOVA model that will adjust for baseline SIB total scores, baseline MMSE-2 scores, age, and gender.

9.5.2 SIB total score from baseline at Week 13

An ANCOVA model as described in Section 9.5.1 will be created to estimate the difference in SIB total scores at Week 13. Again, as with the SIB difference at Week 42. The ANCOVA model will adjust for baseline SIB, baseline MMSE-2 scores, age, and gender.

9.5.3 SIB total scores from baseline at Weeks 9, 20, 24 and 30

The linear regression models using the method of GEE as described in Sections 9.4 and 9.5.2 will be used to estimate the treatment difference in mean SIB total scores from the original baseline (i.e. at screening) at Weeks 9, 20, 24 and 30. As described in Section 9.4, weighted GEE will be used to account for data that are missing at random.

9.5.4 SIB total scores from baseline at Weeks 5, 9, 15, 20, and 24 for subjects with baseline MMSE-2 scores of 10-14 and 15-18

The estimation of the treatment differences at Weeks 9, 20, 24 and 30 for patients within each MMSE-2 group will be based on GEE linear regression model utilizing SIB total scores from baseline at these five time points. As described in Section 9.4, weighted GEE will be used to account for data that are missing at random.

9.5.5 Individual patient's SIB trends over time

For the secondary endpoint of SIB trends over time, individual-specific slopes of total SIB scores will be obtained for all patients. These slopes will be estimated by using SIB data at Week 0, 5, 9, 13, 15, 20, 24, and 28. An overall population averaged slope will then be estimated for each treatment arm, and standard inference methods will be used to test if the mean treatment-specific slopes are 1) statistically different from 0, and 2) statistically different from each other. Both slopes will be considered using absolute SIB total scores as well as SIB total scores from baseline over Weeks 0 to 28.

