
Statistical Considerations:
 
The primary objective for efficacy is to evaluate whether bryostatin is better than the control with respect to the primary and secondary SIB endpoints. Efficacy analyses will be conducted for the full analysis set (FAS), consistent with the modified intention-to-treat principle, defined as all randomized subjects who received at least one dose of randomized study medication and who had at least one post-baseline efficacy assessment.
 
The per protocol analysis set (PP) is defined as all patients completing the study without major protocol deviations. To be included, subjects must have received at least 11 of the 14 doses (80%). The completer analysis set (CAS) will be defined as all randomized subjects who completed two 12-week courses of treatment, and who have a Week 28 SIB assessment. Efficacy analyses will also be conducted for the PP and CAS sets.
 
Adverse event and other safety data will be analyzed descriptively in all subjects who received any dose of study drug (including partial infusions). These data will be summarized by treatment group and by time in study.
		

Eligibility Criteria:**Inclusion**

1. Written informed consent from caregiver and subject (if possible) or legally acceptable representative if different from caregiver
2. Male and female subjects 55-85 years of age inclusive
3. Cognitive deficit present for at least 2 years that meet the diagnostic criteria for probable Alzheimer's dementia.¹ The diagnosis must be confirmed at the time of the screening visit
4. MMSE-2 score of 10-18 inclusive (applies to Screening Visit only)
5. Patients must have a baseline SIB total score of at least 60 and may not have a SIB score >93 at screening
6. Neuroimaging computerized tomography (CT) or Magnetic Resonance Imaging (MRI) within the last 24 months consistent with a diagnosis of probable AD without any other clinically significant co-morbid pathologies. If there has been a significant change in the subject's clinical status since the last imaging study that is not consistent with progression of the subject's AD, an imaging study should be performed to confirm eligibility
7. Reliable caregiver(s) or informant(s) who attends the subject at least an average of 3 hours or more per day for 3 or more days per week and who will agree to accompany the subject to the clinic visits and reliably complete the caregiver questions
8. Adequate vision and motor function to comply with testing

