2.1.1.3 Safety

A total of 116 treatment emergent adverse events (TEAEs) were reported for 47 subjects in the study (43.5%, 47/108). In bryostatin group, 57 AEs were reported by 23 subjects (43.4%, 23/53). In the placebo group, 59 AEs were reported by 24 (43.6%, 24/55) subjects. The majority of AEs were either mild or moderate. A total of 16 related AEs were reported in 11 subjects (10.2%, 11/108). There were 7 related AEs reported for 5 subjects (9.4%, 5/53) in the bryostatin group, and 9 related AEs for 6 subjects (10.9%; 6/55) in placebo group. A total of 15 serious adverse events (SAE) were reported for 11 subjects (10.2%, 11/108) in bryostatin and placebo groups combined. One reported AE in placebo group resulted in death. A total of four AEs led to drug withdrawal in one subject (0.9%, 1/108). A sum total of 12 AEs led to interruption in drug scheduling regimen (4.6%, 5/108). 11 subjects reported 15 SAEs together in bryostatin and placebo groups. However, all of the 15 observed SAEs were considered to be 'unlikely related'

CONFIDENTIAL

to the study treatment. There was one death reported in this study. The subject was randomized to the placebo group and the cause of death is unknown. Details regarding adverse events can be found on ClinicalTrials.gov, study identifier: NCT03560245.

2.1.1.4 *Efficacy*

The primary efficacy endpoint was defined as the change in the SIB total score from baseline to Week 13. Severe Impairment Battery (SIB) scoring is used to assess cognition in subjects with moderate and severe AD and is a useful outcome measure in advanced stages of disease. Forty questions are included with a point score range of 0-100. Lower scores indicate greater cognitive impairment. The mean baseline SIB score of the two randomized populations were 73.7 in bryostatin group and 78.6 for the placebo group. At week 13, the mean SIB score for bryostatin and placebo reached 76.0 and 80.9, respectively. An average increase of 1.3 point and 2.1 points was observed for the bryostatin and placebo groups, respectively at Week 13 and the difference between the treatment groups was not statistically significant.

2.1.1.5 *Summary*

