6.11 Efficacy Analyses

All statistical tests will be performed using a two-tailed 5% overall significance level, unless otherwise stated. All comparisons between treatments will be reported with 95% confidence intervals for the difference.

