6.11.4.5 Individual patient's SIB trends over time

Assessment of slopes in treatment groups and comparison of these slopes will be performed using the MMRM model for primary efficacy analysis, as it described in Section 6.11.2. This approach will be used for absolute SIB values collected from baseline over Weeks 0 to 28 as well as for changes from baseline for these time points:

```
proc mixed data = ;
  class subjid trt01pn avisitn;
  model sibdiff = VAR trt01pn avisitd trt01pn* avisitd / ddfm =
kr outpred = pred;
  repeated avisitn / type = cs subject = subjid;
  estimate "Slope, Bryostatin" time 1 time*trt_no 1 0 / cl;
  estimate "Slope, Placebo" time 1 time*trt_no 0 1 / cl;
  estimate "Slope Difference" time*trt_no 1 -1 / cl;
run;
```

Variables names:

subjid – unique number of subject,

avisitn – visit,

VAR=sib – SIB absolute total score for the first model,

VAR=sibdiff – SIB difference from baseline for the second model,

trt01pn – treatment group.

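### Testing each arm's SIB slope against zero says nothing about bryostatin versus placebo; only the between-arm slope difference should carry inference for this secondary endpoint

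*Protocol*

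**What the plan says.** The Statistical Considerations in the Protocol synopsis set the efficacy question: "The primary objective for efficacy is to evaluate whether bryostatin is better than the control with respect to the primary and secondary SIB endpoints".

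Protocol 9.5.5 estimates a SIB slope for each patient from Weeks 0, 5, 9, 13, 15, 20, 24 and 28, averages the slopes by arm, and then uses standard inference to "test if the mean treatment-specific slopes are 1) statistically different from 0, and 2) statistically different from each other". It does this for both absolute scores and changes from baseline. Under Protocol 9.4, "All statistical tests for efficacy will be two-sided tests", at 0.05.

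SAP 6.11.4.5 keeps both parts: "Assessment of slopes in treatment groups and comparison of these slopes will be performed using the MMRM model for primary efficacy analysis". Its sample code has one ESTIMATE statement for the bryostatin slope, one for the placebo slope and one for their difference, each with confidence limits. Tables 14.2.2.5 and 14.2.2.6 report the results.

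Neither document ranks the two tests or calls the within-arm test descriptive. SAP section 9 lists three changes from the protocol. One removes the false discovery rate control that Protocol 9.5 planned for secondary outcomes. None withdraws the test against zero.

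**The concern.** A within-arm test against zero asks whether SIB changed over time in that arm. It makes no use of the randomised comparison. Anything that moves both arms together makes its null false, whether or not bryostatin works.

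The sponsor's own data show that shared movement is plausible. In study NTRP101-203 (Protocol 2.1.1.4), "An average increase of 1.3 point and 2.1 points was observed for the bryostatin and placebo groups, respectively at Week 13". Both arms rose, placebo by more, and the difference was not significant. In study NTRP101-201 (Protocol 2.1.3.3), MMSE-2 scores improved in both groups, and the protocol puts this down mostly to practice effects. In the present trial the SIB is given at screening and at eight scheduled visits after that.

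Two misreadings are at stake. A significant bryostatin slope could be presented as a positive result on a declared secondary efficacy endpoint. Or chance could make one arm significant and the other not, inviting the reading that patients improved on drug but not on placebo.

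**Working it through.** **Inputs.** From Protocol 9.0: sigma = 5.3, rho = 0.5, m = 50 per arm (40 with the stated 20% dropout), n = 8 visits, s_x² = 127, d = 0.15 points/week. Two-sided 5% level. Visits as listed in Protocol 9.5.5.

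**The plan's own figure.** Solving Eq 1 for power, SE(difference) = sqrt(2σ²(1−ρ)/(m·n·s_x²)).
- m = 50: sqrt(2 × 28.09 × 0.5 / (50 × 8 × 127)) = 0.0235. Then 0.15/0.0235 = 6.38, and power = Φ(6.38 − 1.96), above 99.99%.
- m = 40: SE = 0.0263, power 99.99%.

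The stated power of over 99% reproduces. It concerns the between-arm difference.

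**Time spread from the listed visits.** The weeks sum to 114 and their squares to 2260, so Sxx = 2260 − 114²/8 = 635.5. That is 79.4 per visit (90.8 with divisor n − 1), not 127. Between-arm power is still 99.9% (m = 50) and 99.5% (m = 40). I use 635.5 below because it gives less extreme results. With 127 the within-arm SE would be 0.0166 instead of 0.021.

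**Within-arm test.** SE(one arm) = sqrt(σ²(1−ρ)/(m·Sxx) + SD²/m), where SD is the between-patient SD of true slopes.
- SD = 0: sqrt(14.045/(50 × 635.5)) = 0.021 points/week.
- SD = 0.30: sqrt(0.000442 + 0.09/50) = 0.047 points/week.

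**Drift scenarios.** The study 203 placebo gain gives 2.1/13 = 0.16 points/week if it continues to Week 28. The same 2.1 points spread over 28 weeks gives 0.075. A smaller value, 0.05, is added (1.4 points by Week 28). All are assumptions, as is the slope SD.

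**Rejection rates when the two arms have the same true slope.** Simulated, 50 per arm, full data, least-squares slope per patient, one-sample t-test within arm and two-sample t-test between arms:

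| Shared drift (points/week) | Versus 0, slope SD 0 | Versus 0, slope SD 0.15 | Versus 0, slope SD 0.30 | Between arms |
|---|---|---|---|---|
| 0 | 5% | 5% | 5% | about 5% |
| 0.05 | about 65% | 37% | 19% | about 5% |
| 0.075 | about 93% | 68% | 33% | about 5% |
| 0.16 | near 100% | 100% | 92% | about 5% |

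Exact t-test calculations from the SE formula agree with the within-arm figures to about one percentage point. At 40 per arm with SD 0, the rates are 55% (0.05), 88% (0.075) and 100% (0.16). At an assumed SD of 0.40 with 50 per arm, they fall to about 23% at 0.075 and 75% at 0.16.

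**One arm significant, the other not.** The arms are independent, so this has probability 2p(1−p), where p is the within-arm rejection rate. It peaks at 50% when p = 0.5. At p = 0.65 it is 2 × 0.65 × 0.35 = 46%. In half of these trials the significant arm is bryostatin.

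**Downward drift.** At −0.036 points/week (about 1 point lost by Week 28), the test against zero rejected in 9% to 39% of simulated trials across slope SDs of 0.40 down to 0. A significant positive slope occurred in at most 0.6%.

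**Limit of the check.** It follows the per-patient slopes of Protocol 9.5.5. The SAP's mixed model was not simulated; its printed ESTIMATE statements use variable names that are not in its MODEL statement, so I rely on their evident intent.

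**The case against.** The strongest reply is that the randomised comparison is already planned. The sentence that sets up the test against zero also sets up the comparison of slopes, and the SAP has an explicit difference contrast. The synopsis and the hypothesis in Protocol 3.1 both define efficacy relative to control or placebo, and no passage makes a within-arm slope a success criterion. This stands. A reader might infer that the endpoint is tested against zero instead of against placebo; the documents do not support that.

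A reader might also infer that the bryostatin slope will usually be significant even if the drug does nothing. That is not established either. The 28-week drift and the slope SD are not given. Continuing the study 203 placebo rate to Week 28 implies a shared gain of 0.16 × 28 = 4.5 points, more than the plan's own 4-point clinically significant difference, in a progressive dementia. Study 203 also stratified on MMSE-2 scores of 4-9 and 10-15, while this trial enrols 10-18. Under a downward drift the significant finding would be a decline, not a false benefit.

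Two further points have some force. SAP 6.11.4.5 names no hypothesis test against zero, asks for confidence limits and takes precedence over the protocol's analyses. But SAP section 9 does not list the test as dropped, and ESTIMATE output normally includes a p-value; the table shells are not available to settle this. Protocol 3.1 also counts only improvement from baseline as clinically significant, and a difference alone cannot separate improvement from slower decline. A per-arm slope with its CI supplies that information without a p-value.

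**Conclusion.** The concern holds for the first of the two slope tests. That test carries no information on drug versus placebo, yet it is planned as formal inference under a declared secondary efficacy endpoint, unranked and without the multiplicity control the protocol had promised. With no drug effect its rejection rate runs from 5% at zero drift to near 100% at 0.16 points/week. At 0.05 to 0.075 it is about 65% to 93% with no slope variation and 19% to 33% with a slope SD of 0.30. These figures assume linear drift common to both arms, full data and 50 per arm, with drift and slope SD supplied by assumption. The between-arm slope test holds its 5% level, and the primary Week 28 analysis and the sample size are unaffected. The matter is confined to what may be concluded from this one secondary endpoint.

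**What to change.** In Protocol 9.5.5 and SAP 6.11.4.5, make the between-arm slope difference the only inferential test of this endpoint. In Tables 14.2.2.5 and 14.2.2.6, report each arm's slope as a descriptive estimate with a 95% CI and no p-value. Add a sentence stating that no efficacy conclusion will be drawn from a within-arm slope, or from one arm being significant and the other not.

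The cost is a wording change in two documents and the suppression of any within-arm p-values in two tables. No new data or patients are needed. What is lost is a set of within-arm p-values that cannot support a treatment claim.
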